## Study Outcomes

For the Main Study, all data collection for both DirectCAM and TeleCAM participants was conducted using standardized protocols and was performed by a therapist or therapist assistant at each clinic site who was not involved in the intervention delivery. In addition, demographic (age, sex, and race) and clinical characteristics (health history, disease severity via PDDS, heart rate, and blood pressure) were assessed.

**Primary Outcomes.** The primary outcomes of interest to our stakeholders included changes in fatigue, pain, quality of life, and physical activity. Fatigue was assessed using the Modified Fatigue Impact Scale, pain assessed using SF-36 pain subscale and quality of life via SF-36 questionnaire's physical component and mental component scores. Physical activity was measured using the GLTEQ. Note that the scales and questionnaires were self-reported by the participants.

*Modified Fatigue Impact Scale (MFIS).* The MFIS consists of 21 items that assess the effects of fatigue related to physical, cognitive, and psychosocial functioning. It is a

modified version of the Fatigue Impact Scale. The scale has been widely used in MS research.

**SF-36.** The SF-36 is a widely used questionnaire that assesses aspects of health-related quality of life. It contains eight subscales including: energy/fatigue, physical functioning, bodily pain, general health perceptions, role limitations due to physical health problems, role limitations due to personal or emotional problems, social functioning, and emotional well-being. Scores range from 0 to 100, with lower scores indicating more disability. From these eight scales, 2 composite scores: physical component score (PCS) and mental component score (MCS) were calculated by multiplying each subscale with specific weights. These 2 scores are measuring QOL.

**Secondary Outcomes.** The secondary outcomes were changes in functional scores for balance, endurance, gait, and strength. These tests were assessed by therapists at the clinic for both DirectCAM and TeleCAM participants.

*Berg Balance Scale (BBS).* The BBS is administered by a single rater who scores an individual's balance performance from a value of 0 (cannot perform) to 4 (normal performance) on a total of 14 tasks. Tasks incorporate several activities related to static balance such as sitting to standing, retrieving an object from the floor, standing with eyes closed, and standing on one foot. The test was administered with a ruler, two chairs (height: 45–47 cm; one with armrests and one without), a footstool, a 15-foot walkway, and a stopwatch. Previous research has reported a minimum detectable change of seven points in multiple sclerosis.

*Five Time Sit To Stand (FTSTS).* The FTSTS was used to assess balance, it measures the amount of time it takes for an patient to transfer from a seated position to standing position and back to sitting five times. The FTSTS test has been shown to effectively assess lower extremity strength in individuals with MS. Furthermore, its reliability and validity have been established in various other neurological disorders such as stroke and Parkinson's disease.

*Six Minute Walk Test (6MWT).* The 6MWT was used to assess walking endurance, in which total distance traveled over 6-minute period was recorded in meters. The test was administered in a hallway with an unobstructed 50-foot path marked with two cones. Perception of fatigue was measured and recorded with the BORG Rating of Perceived Exertion (RPE) before and after the test. The test has been reported to have excellent test-retest (ICC = 0.97) in the stroke population and people with MS and has known validity for use in measuring endurance in persons with MS.

*Timed Up and Go (TUG).* The TUG test was used to assess mobility and balance, which involves recording the time required to rise from a chair, walk to a 3-meter mark, turn around, walk back to the chair, and sit down. The test is a valid test of mobility, balance, and walking ability in people with MS, with excellent test-retest reliability (ICC = 0.96).

*Grip Strength Hand Dynamometer.* Hand grip strength was measured using a hand dynamometer with the dominant and non-dominant hands. The mean of three trials for each hand was used as the actual score. The test was conducted with the participant sitting in a chair, shoulder adducted and neutrally rotated, elbow by their side and flexed

to a 90° angle, and forearm and wrist in neutral position. Grip strength has previously shown a high interrater reliability and test-retest reliability in persons with MS.

*Time 25 Foot Walk.* T25FW is commonly administered within the MS functional composite (MSFC), and it has also been employed independently in clinical investigations. It is a quantitative mobility and leg function performance test based on a timed 25-walk. The patient is guided to a designated starting point on a clearly outlined 25-foot walk and is advised to walk the distance as swiftly as they can while ensuring safety. Timing begins when the instruction to commence is given and concludes once the individual reaches the 25-foot mark. The process is repeated immediately with the individual walking back the same distance. Participants are permitted to utilize assistive devices during this activity.

**Mediators.** Four mediators were assessed to address the tertiary aim.

*Social provision scale (SPS).* The SPS was used to assess the degree to which a participant perceived his or her social relationships and various dimensions of social support. The scale has been validated in people with MS.

[figure not shown]
*Exercise Self-Efficacy (EXSE):* The EXSE measures self-efficacy related to physical activity and consists of 6 items that assess an individual's belief in their capability to participate in moderate physical activity for at least 20 minutes, three times a week, within one-month intervals. Participants rated each item on a scale from 0 (not confident at all) to 100 (completely confident) and the scores were averaged to create a composite score ranging from 0 to 100. Higher scores indicate higher levels of confidence in regularly engaging in physical activity.

*Exercise Goal-Setting Questionnaire (EGSQ):* The EGSQ comprises 10 items that assess goal-setting behaviors for exercise. Participants rated each item on a 5-point scale ranging from 1 (does not describe) to 5 (describes completely). The scores of the individual items were then added together to calculate an overall score, ranging from 10 to 50. Higher scores on the EGSQ indicate a greater inclination towards setting goals for engaging in physical activity.

*Multidimensional Outcome Expectations for Exercise Scale (MOEES):* The MOEES was used to assess outcome expectations for exercise. The scale consists of 15 items representing three subdomains of outcome expectations: physical, social, and self-evaluative. Within these subdomains, six items pertain to physical outcomes, four items to social outcomes, and five items to self-evaluative outcomes. Participants rated each of the 15 items on a 5-point scale, ranging from 1 (strongly disagree) to 5 (strongly agree). The scores for each subscale were then added together, resulting in three separate scores reflecting physical, social, or self-evaluative outcome expectations. Higher scores in each subscale indicate a stronger belief in the expected positive outcomes related to physical, social, or self-evaluative aspects of exercise.

**Figure 3** shows mediation model with the effect of 4 Social Cognitive Theory (SCT) construct variables as mediating variables.

**Figure 3. Illustration of the mediation analysis:**

X: the independent variable, *c*: the coefficient relating the independent variable and the dependent variable, *c'*: the coefficient relating the independent variable to the dependent variable adjusted for the mediator, *b*: the coefficient relating the mediator to the dependent variable adjusted for the independent variable, *a*: the coefficient relating the independent variable to the mediator.

**Table 3** provides an overview of the primary, secondary, and exploratory outcomes and the frequency and mode of data collection. To further tailor our intervention, the T25FW test was administered. In addition, the Dynamic Gait Index (DGI) was administered at clinic sites that had uniform steps to assess the test and compare its utility with BBS. However, these were exploratory outcomes and were not part of our original proposal; Hence, they were not accounted for while developing power calculations for the study in terms of the number of multiple comparisons for the family wise error rate.

**Table 3. TEAMS Study Outcome Measures**

Variables	Instrument	Role, Frequency, Mode of Collection
Fatigue	Modified Fatigue Impact Scale	Primary Outcome
Pain	SF-36 PCS	Baseline, 3 rd , 6 th and 12 th month
Quality of life	SF-36 MCS	Self-reported
Physical activity	Godin Leisure Time Exercice Questionnaire 	Secondary Outcome
Balance	Berg Balance Scale 	

	Five Time Sit to Stand 	
Gait	Timed Up & Go (TUG)  Time 25 Foot Walk 	Baseline, 3rd, 6th and 12th month  At the clinic (for Main study)
Endurance	6-minute Walk Test (6MWT) 	
Strength	Hand-held Dynamometer/Grip Strength 	
Quality of life	SF-36 Physical functioning, Pain, Energy/Fatigue, Emotional wellbeing, Role limitation due to physical health, Role limitation due to emotional health, Social functioning, General health	Exploratory outcomes  Baseline, 3 rd , 6 th and 12 th month  Self-reported
Gait	Dynamic Gait Index Scale	Exploratory outcomes  Baseline, 3 rd , 6 th and 12 th month  Objective outcomes
Outcome expectations for exercise	Multidimensional Outcome Expectations for Exercise Scale (MOEES) 	Mediators  Baseline, 3 rd , 6 th and 12 th month
Exercise self-efficacy	Exercise Self-efficacy Scale 	
Social support for exercise	Social Support and Exercise Survey 	
Exercise self-regulation	Exercise Goal-setting Scale 	

IVR: Interactive Voice Response.

## Enhancement Study

Outcome measures for the Enhancement study were collected using teleassessment via the remote platform. To ensure strong fidelity across therapists, each therapist underwent extensive training on use of the technology, risk management for remote assessment and intervention, and teleassessment and intervention protocols. The goal of the protocols was to mirror onsite clinic assessments and intervention. The measures utilized were based on the

participants' PDDS score. Participants with a PDDS score between 0-4 (indicative of minimal mobility disability) completed the following measures: Grip strength test, Five Times Sit to Stand test, TUG, and BBS. Participants with a PDDS score between 5-7 completed all measures except the TUG and BBS due to safety concerns (potential risk of falling) of performing these tests at home. The teleassessment equipment provided to participants in the Enhancement study is outlined in **Table 4**. For safety considerations, rDirectCAM participants who had a PDDS score of 5, 6, and 7 were not given any tests related to ambulation. Hence, two different sets of equipment were provided: one for participants with a PDDS score of 0-4 and another for participants with a PDDS score of 5-7. More details of the teleassessment are presented in the Appendix D.

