## **Participants**

The study population included people with MS in the states of Alabama, Mississippi, and Tennessee. Interested participants were enrolled if they self-reported a diagnosis of MS, with a PDDS score between 0 and 7. The PDDS is an ordinal scale ranging from 0 (Normal) to 8 (Bedridden). It is a simple and practical tool for measuring self-reported disability status for people with MS and has a strong correlation ( $rs=0.8$ ) with the Expanded Disability Status Scale (EDSS). Additional inclusion criteria included ages of 18 to 70 years, able to use arms and legs for exercise, and physician clearance. Exclusion criteria included: 1) significantly impaired acuity that prevented seeing a tablet screen to follow home exercise program; 2) cardiovascular disease event within the past six months, severe pulmonary disease, renal failure; 3) active pressure ulcer; 4) currently pregnant; 5) within 30 days of receiving an exercise or rehabilitation program; 6) Godin Leisure Time Exercise Questionnaire (GLTEQ) score  $\geq 24$ .

The GLTEQ contains two questions. The first question asks participants to report weekly frequencies of activities they perform at different intensities. A total weekly leisure activity is a sum of activity scores calculated by multiplying the weekly frequencies of strenuous, moderate, and light activities by 9, 5, and 3, respectively. The second question asks participants the

frequency of weekly leisure-time activities performed that are long enough to work up a sweat.

The scale has been validated and used in previous research with people with MS.

Adverse events (AEs) were monitored following types defined by the Behavior Change Consortium of the National Institutes of Health, which included: falls, cardiovascular-related episodes, musculoskeletal-related events and health care use. The study was approved by the Institutional Review Board of the institution and was conducted in accordance with a clinical trial protocol registered at ClinicalTrials.gov.

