### Interventions and Comparators or Controls

The two study arms received the same CAM intervention, and the comparison was between the on-site delivery (DirectCAM) versus the asynchronous delivery (TeleCAM). The CAM intervention is a 12 week intervention (3 month) composed of 20 sessions that were structured into two segments: the first 8 weeks consisted of two 1-hour sessions per week that included 3 components: 20-minute yoga exercise routine; 20-minute Pilates exercise routine; and a 20-minute routine of dual tasking and functional exercises that involved multifaceted training such as multidirectional upper extremity reaching while carrying on a conversation, and ball bouncing while tracking the ball with head and eye movements. From weeks 9 to 12, the intervention transitioned to one session per week that focused on yoga and Pilates. The intervention was adapted and tailored toward the functional level of each participant, determined by the time it took for participants to complete the Timed 25-Foot Walk (T25FW) test. There were 4 functional levels provided. A participant who had a T25FW score of less than 6 seconds was assigned to TEAMS 1, a T25FW score of 6 to 7.99 seconds was

TEAMS 2, a T25FW score of more than 8 seconds was TEAMS 3, and if unable to complete the T25FW, TEAMS 4 was assigned. If the participant self-reported a diagnosis of osteoporosis and was able to complete the T25FW, they were assigned to TEAMS 3-OP. Those with a diagnosis of osteoporosis that were unable to complete the T25FW were assigned to TEAMS 4-OP. TEAMS 1 and TEAMS 2 completed the intervention exercises in prone, supine, long sitting, standing, and quadriped. TEAMS 3 and TEAMS 3-OP completed the exercises in a chair and with an assistive device for support in standing. TEAMS 4 and TEAMS 4-OP completed all the exercises in a chair. All TEAMS levels included ways to tailor the exercises to better align each participant's functional level. **Figure 2** demonstrates examples of the exercises and adaptation of the CAM intervention.

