**Table 2. Exercise Equipment by TEAMS Level**

Equipment	TEAMS Level 1	TEAMS Level 2	TEAMS Level 3	TEAMS Level 4
Racquet Ball	✓	✓	✓	✓
Yoga Strap	✓	✓	✓	✓
Theraband	✓	✓	✓	✓
Pilates Disc	✓	✓	✓	✓
Sliders	✓	✓	✓	✓
Yoga Mat	✓	✓	✓	✓
Yoga Block	✓	✓	✓	
Physioball	✓	✓	✓	
Half Roll	✓	✓		
Tablet (TeleCAM)	✓	✓	✓	✓
Tablet Case (TeleCAM)	✓	✓	✓	✓
Tablet Stand (TeleCAM)	✓	✓	✓	✓

TEAMS: Tele-Exercise and Multiple Sclerosis, CAM: Complementary and Alternative Medicine, T25FW: Time 25 Foot Walk score. TEAMS level 1: T25FW <6 seconds, TEAMS level 2: T25FW 6-7.99 seconds, TEAMS level 3: T25FW >8 seconds, TEAMS level 4: unable to complete T25FW.

For the Enhancement study, participants received an additional set of equipment (in addition to the exercise equipment) that was shipped to their home for completing the teleassessment protocol. The teleassessment equipment provided to participants in the Enhancement study is outlined in Table 3. For safety considerations, rDirectCAM participants who had a PDDS score of 5, 6, and 7 were not given any tests related to ambulation. Hence, two different sets of equipment were provided: one for participants with a PDDS score of 0-4 and another for participants with a PDDS score of 5-7.

**DirectCAM.** DirectCAM participants were asked to work with a therapist at the assigned clinic to complete the 20 one-hour training sessions as described in **Figure 2**. A therapists training manual and a DirectCAM session checklist were used to ensure intervention fidelity across therapists (see Appendices A and B). At the end of the 12-

week intervention, the DirectCAM participants received a set of instructions and handouts (see Appendix C) with photos demonstrating the exercises and were asked to continue the program in their home for up to one-year post-intervention initiation (i.e., 9 months after the completion of the intervention delivered at the clinic).

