### Potential covariates

In addition to age, sex, education-level, height, and race, which were collected at baseline, information on all participants' time-varying covariates were collected through a questionnaire at baseline and the three follow-up time points. These covariates included: weight, type of MS, prescribed and non-prescribed medications, distance from the clinic

(address), caregiver support, assisted devices, PDDS. The type of MS, PDDS, age and geographic locations based on participants zip code (urban/non-urban) were our prespecified moderators for the study outcomes.

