### **Enhancement Study**

We used a quasi-experimental design to compare rDirectCAM with DirectCAM. Our hypothesis posits that the observed difference in outcome effects between rDirectCAM and DirectCAM is less than a predetermined non-inferiority margin ( $-\Delta$ ). These margins were selected based on the MCID or minimal detectable change (MCD) of the studied outcomes among MS population published in literature (MFIS= 4, BBS= 3, TUG= 10.6, FTSTS= 13, Grip-strength= 10.5, SF-36 Physical functioning= 7.1 and SF-36 pain= 4.9).

Specifically, we hypothesized that the effect of rDirectCAM was not inferior to that of DirectCAM by a margin that was considered clinically acceptable, thereby affirming the non-inferiority of rDirectCAM in comparison to DirectCAM. In other words, if the resulting *p*-value was significant, this would mean that we rejected the null hypothesis which stated that the difference in the effect between two arms were more than the non-inferiority margin. Statistical significance level of 0.05 and at confidence interval 95%, same as superiority trials,

was applied to determine non-inferiority. To achieve a balance between the study arms, several analyses involved regression-based parametric adjustment measures that are sensitive to model misspecification. Propensity scores are another widely used measure to achieve balance or matching between the study arms. These scores model the probability of being assigned to the given treatment conditional on observed baseline covariates obtained via measures including matching, inverse probability treatment weighting (IPTW), and stratification and covariate adjustment. Matching-based measures such as nearest neighbor matching algorithm often led to study participants being excluded when a match was not available. This may have potentially biased the effect estimates. When this occurred, we utilized stabilized IPTW, a non-parametric balancing strategy, to achieve balance between the two study arms (rDirectCAM and DirectCAM). Using this weighted analysis, we modeled the causal parameter as the inverse of the conditional probability of receiving the treatment given the observed covariates, a technique that provides asymptotically unbiased estimates and uses data on all available study participants across the two arms.

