Our general analytic approach was to leverage the linear mixed modeling framework to account for repeated nature of data. Appropriate contrasts were applied using the fitted model. Sensitivity analyses were performed to assess distributional and other modeling assumptions. Missing data was imputed using multiple imputation where necessary. The non-inferiority ( $-\Delta$ ) of the rDirectCAM was assessed by comparing the lower limit of confidence interval for each outcome to its corresponding margin so that if the lower bound was above this margin, then the rDirectCAM was deemed non-inferior. For the MFIS and TUG assessments, wherein an elevated score signified a deterioration in the outcome, we juxtaposed the upper limit of the

confidence interval against a predefined margin. Non-inferiority was deemed established when the upper bound was less than  $-\Delta^{133}$ .

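### In the Enhancement study, BBS and TUG exist only for PDDS 0-4 in rDirectCAM, but nothing restricts the DirectCAM comparator to that range, so the two non-inferiority contrasts could compare different disability mixes

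*Combined protocol and SAP*

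**What the plan says.** All references are to the combined protocol and SAP.

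- **rDirectCAM testing.** The Enhancement Study text under Study Outcomes states: "Participants with a PDDS score between 5-7 completed all measures except the TUG and BBS due to safety concerns". The Interventions section, after Table 2, gives the rule more broadly: "rDirectCAM participants who had a PDDS score of 5, 6, and 7 were not given any tests related to ambulation". Table 4 agrees: the PDDS 5-7 kit has no tape measure, cone or wall tape.
- **DirectCAM testing.** Participants were eligible "with a PDDS score between 0 and 7". On the functional outcomes, Study Outcomes says: "These tests were assessed by therapists at the clinic for both DirectCAM and TeleCAM participants". It states no PDDS limit.
- **Contrasts.** The Enhancement Study part of Analytical and Statistical Approaches compares rDirectCAM with DirectCAM without randomisation. Its non-inferiority margins include 3 for BBS and 10.6 for TUG.
- **Balancing.** The same section turns to stabilised inverse probability weighting where matching would exclude people, and says the technique "uses data on all available study participants across the two arms". It does not name the propensity covariates.
- **Missing data.** "Missing data was imputed using multiple imputation where necessary". There is no separate rule for values that are missing by design.
- **PDDS as a modifier.** Potential covariates says: "The type of MS, PDDS, age and geographic locations based on participants zip code (urban/non-urban) were our prespecified moderators for the study outcomes". It also lists PDDS among the time-varying covariates. The only PDDS split in the analysis text is 0-3 versus 4-7, for the Main study moderators, and it does not match the 0-4 versus 5-7 testing cut.

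**The concern.** A non-inferiority contrast needs the two arms to be comparable among the people who supply the outcome. For BBS and TUG, rDirectCAM supplies nobody at PDDS 5-7, while DirectCAM, on the text as written, supplies people across PDDS 0-7. If mean change differs between the two disability ranges, part of the estimated arm difference is disability mix.

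The direction is not known. If DirectCAM participants at PDDS 5-7 improve less than those at PDDS 0-4, they pull the comparator mean down and rDirectCAM looks better than it is. If they improve more, rDirectCAM looks worse. A non-inferiority verdict could therefore be wrong either way.

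Whether or not bias is present, the rDirectCAM evidence on these two outcomes covers PDDS 0-4 only, and nothing in the analysis text limits the conclusion to that range.

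**Working it through.** **The plan's own figure.** The one sample-size figure here is 55 completers inflated for 25% attrition: 55 / 0.75 = 73.3, rounded up to 74. This matches the plan. It was sized on MFIS, which this point does not affect.

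**Does the planned method remove the mismatch?** Take each route in turn.

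1. *Weights fitted on all participants.* Assume PDDS 5-7 shares of 30% in DirectCAM and 20% in rDirectCAM, and a 5:1 arm ratio. The ratio is an assumption: half of the Main study's 533 planned completers over 55 is 266.5 / 55 = 4.8. Stabilised weights bring each arm to the pooled share, (5 × 0.30 + 1 × 0.20) / 6 = 28.3%. Among those with a BBS or TUG value, the shares are 28.3% in DirectCAM and 0% in rDirectCAM. With no true arm effect and a 2-point gap in change between strata, the spurious difference is 0.283 × 2 = 0.57. At a 1:1 ratio the pooled share is 25% and the difference 0.50. With both arms restricted to PDDS 0-4 it is 0.
2. *Weights refitted only in those measured.* No rDirectCAM participant is then at PDDS 5-7, so positivity fails in that stratum. DirectCAM participants there still receive the stabilised weight P(DirectCAM) / 1, which is above zero. With the same inputs, their weighted share is (5 × 0.30) / (5 + 0.80) = 25.9%.
3. *Matching.* A pair matched at PDDS 5-7 has only the DirectCAM outcome. No rule says that such pairs are dropped.
4. *Multiple imputation.* No rDirectCAM BBS or TUG value exists at PDDS 5-7. An imputation model would have to carry the arm effect over from PDDS 0-4, which is extrapolation.

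**Size.** Let *f* be the share of tested DirectCAM participants at PDDS 5-7, and *d* the difference in mean change between PDDS 5-7 and PDDS 0-4. DirectCAM's mean change moves by *f × d* and rDirectCAM's does not, so the bias has size *f × d*. The documents give neither input; the ranges below are assumptions.

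| Outcome (margin) | Assumption | Result |
|---|---|---|
| BBS (3) | *f* 20%, *d* 1 | 0.2 points; 0.2 / 3 = 7% of margin |
| BBS (3) | *f* 40%, *d* 3 | 1.2 points; 1.2 / 3 = 40% of margin |
| TUG (10.6) | bias of 10% of margin (1.06), *f* 40% | needs *d* = 1.06 / 0.40 = 2.65 |
| TUG (10.6) | same, *f* 20% | needs *d* = 1.06 / 0.20 = 5.3 |

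The TUG shares may be too high. Under Interventions, "if unable to complete the T25FW, TEAMS 4 was assigned", and DirectCAM participants at that level may also have no TUG time. If half of those at PDDS 5-7 have none, *f* falls from 40% to 0.20 / 0.80 = 25%, and from 20% to 0.10 / 0.90 = 11.1%. The gap needed to reach 10% of the margin then becomes 1.06 / 0.25 = 4.2 to 1.06 / 0.111 = 9.5.

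**Using up the whole margin.** At *f* = 40% the gap would have to be 3 / 0.40 = 7.5 BBS points or 10.6 / 0.40 = 26.5 TUG units. At 20% it would be 15 and 53.

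**Numbers available.** If 20-40% of rDirectCAM is at PDDS 5-7 (also assumed), then 55 × 0.80 = 44 down to 55 × 0.60 = 33 of the planned completers have BBS or TUG.

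**The case against.** The strongest reply is that this argues from silence. The plan does not define the DirectCAM analysis set for BBS or TUG, so a PDDS 0-7 comparator is inferred. The remark about using all available participants describes weighting in general, by contrast with matching, and is not a population rule for these outcomes. That is fair, and it is why the point is put conditionally. But no route described in the plan produces the missing stratum.

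Other objections have partial force:

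- **Moderator evidence.** The moderator analyses cover only self-reported outcomes, and compare TeleCAM with DirectCAM. What matters here is whether change in BBS or TUG within DirectCAM depends on PDDS, and the plan does not say that it does. Naming PDDS as a moderator shows plausibility only. So does the tailoring of exercise content to walking ability, with TEAMS 4 exercising entirely in a chair.
- **Remote DirectCAM testing.** The March 2020 changes suspended onsite visits and moved some DirectCAM participants to remote testing; 25 had started the intervention. If the home-testing rule also applied to them, the mismatch narrows, but the text does not say so. Appendix D, which holds the teleassessment details, is not in the text reviewed.
- **Change scores.** The contrast is on change, so baseline level differences partly cancel. Differences in change do not.
- **Consequence.** Only two secondary outcomes are involved, and the testing restriction is openly stated. What is missing is its carry-over into the analysis and the conclusion.

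**Conclusion.** The concern holds as a conditional one. The plan sets two non-inferiority contrasts in which one arm has no outcome data at PDDS 5-7 by design, and it does not restrict the other arm to match. Whether this biases the results depends on the PDDS mix of tested DirectCAM participants and on whether their change differs by PDDS. Neither can be read from the documents, so size and direction are unknown.

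On the illustrative range, the shift could change a close BBS verdict but would not by itself use up the margin. TUG needs a much larger gap to matter, so the risk is mainly to BBS. MFIS, FTSTS, grip strength and the SF-36 outcomes are not affected by this omission. The limit on what can be claimed, PDDS 0-4 only, applies whatever the bias.

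**What to change.** For BBS and TUG in the Enhancement study:

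1. Restrict both arms to baseline PDDS 0-4. Because PDDS is time-varying, state which visit's score decided testing and how participants who crossed the cut are handled.
2. Refit the propensity model and weights in that subset, with baseline PDDS among the covariates.
3. Do not impute BBS or TUG for rDirectCAM participants at PDDS 5-7.
4. Report the numbers analysed per arm, and word both conclusions as applying to PDDS 0-4.
5. State whether DirectCAM participants tested remotely after March 2020 came under the same home-testing restriction.

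If the comparator was already restricted, a sentence saying so settles the comparability question; item 4 still applies.

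The cost is a re-run of existing code on a subset, fewer DirectCAM comparators, and a narrower claim for two secondary outcomes. No new data are needed. If baseline PDDS governed testing, no observed rDirectCAM BBS or TUG value is lost. The home-testing safety rule is unchanged.
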